In recent years, various international consensuses have brought these fundamental concepts to the clinical practice. The European Working Group on Sarcopenia in Older People (EWGSOP) developed a practical clinical definition and consensus diagnostic criteria for age-related sarcopenia, recommending the use of the presence of both low muscle mass and low muscle function (strength or performance) for diagnosis. Recently, a new consensus (EWGSOP2) recommended low muscle strength as the primary parameter to assess sarcopenia and new

[figure not shown]
cut-off points to increase harmonization of sarcopenia studies (15).

Given the above, there is an ongoing intensive search for novel therapies, including dietary ones that can attenuate the loss of muscle mass and strength in the elderly (10, 16). Interestingly, a growing body of research indicate that nutritional factors can preserve muscle function from age-related decline. In particular, phenolic compounds, widely distributed in fruits including grapes, have shown beneficial effects in muscle health (17, 18). Phenolic compounds have garnered attention because they ability to alleviate disease pathologies through anti-inflammatory, anti-carcinogenic and antioxidant

properties. However, the exact influence of grapes and grapes phenolic compounds mitigating sarcopenia in humans remains unexplored.

A novel and understudied mechanism by which skeletal muscle might mediate their protective effect against sarcopenia is by secreting myokines. Irisin is a myokine regulated by peroxisome proliferator-activated receptor gamma co-activator-1 α (PGC-1 α) and released into the bloodstream after cleavage of the Fibronectin type III domain-containing protein 5 (FNDC5) (**Fig 1.**). Recent studies have indicated that circulating irisin can promote skeletal muscle growth (12, 19, 20). Lower irisin concentrations have been observed in sarcopenia patients (21) and dialyzed patients with cardiovascular disease (22). Furthermore, lower irisin plasma levels are associated with sarcopenia in postmenopausal women (10).

In a recent study, we have shown that phenolic compounds present in a grape pomace extract (GPE), prevent irisin downregulation in rats fed a high-fat diet and in L6 myotube cells. In particular, we documented that consumption of the GPE activates the FNDC5/irisin pathway, with a significant increase of PGC-1 α and FNDC5 protein

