levels compared to control and high fat diet groups (**Figure 2A-B**). Furthermore, supplementation with GPE led to the increase in irisin plasma level (**Figure 2C**)(11).

In order to understand the underlying mechanism involved in the GPE-related irisin increased levels, we next evaluated the effects of epicatechin, one of the main flavonoids present in GPE, in L6 myotubes challenged with palmitate, to mimic a condition of fatty acids oversupply. Protein levels of PGC- 1 α and FNDC5 were significantly higher in the EC and palmitate-treated cells, compared with palmitate-treated cells (**Figure 3A-B**). The same tendency was observed by immunocytochemical analysis of PGC-1 α , while no differences were observed in FNDC5 fluorescence intensity among treatments (**Figure 3D-E**). In addition, EC induced a 2-fold increase in irisin levels secreted to the medium compared with cells treated with only palmitate (**Figure 3C**). These data strongly indicate that phenolic compounds enhance irisin levels in vitro and in vivo.

These intriguing data allow us to hypothesize that phenolic compounds present in grapes might have a positive effect in human health, specially preventing sarcopenia in elderly humans, in part, by increasing irisin levels.

4) Enrollment Numbers

We chose the “changes in plasma irisin levels” as our primary outcome to determine the power calculations for sample size. Based on our preliminary data (11), 5 individuals per group are required to reach 80% power to detect differences in irisin levels between the groups, at a $\alpha=0.05$, using a two-sided paired T-test. We propose to enroll 7 individuals per group, instead of 5, in the event of a patient drop out of the study (for any unforeseen circumstances). In total we will have 14 subjects.

5) Inclusion and Exclusion Criteria

Inclusion Criteria: postmenopausal women aged 60 years or older with a hand-grip strength media value of 16 kg or lower, normal body mass index (BMI) with values between 18.4 and 24.9 kg/m², blood pressure below 130/80 mmHg, and plasma glucose and cholesterol concentrations below 100 and 200 mg/dl.

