Return stool and urine collection kit			X	X
Adverse events assessment			X	X

After confirmation of the inclusion/exclusion criteria enrolled subjects will be asked to travel to Ragle Human Nutrition Center at University of California Davis for 3 study visits: a baseline visit (**visit 1**), and a 3-week intervention visit (**visit 2**) and a final 6-week visit (**visit 3**)

Visit 1 (baseline visit):

On this visit, baseline measurement will be done. Fasted participants (12 h) will provide blood samples and complete two tests:

Blood samples: from each participant 20 ml of blood will be extracted. The following parameters will be measured in plasma, (the same parameters will be measure in the following visits 2 and 3):

Blood parameter	Volume of blood needed	Visit 1	Visit 2	Visit 3
Irisin	1200 ul	X	X	X
Glucose	1000 ul	X	X	X
Insulin	1200 ul	X	X	X
GLP-1/ 2, GIP	2000 ul	X	X	X
Adiponectin, leptin and ghrelin	3000 ul	X	X	X
Blood urea nitrogen, creatinine	1000 ul	X	X	X
Total cholesterol, triglyceride, high-density lipoprotein (HDL), low-density lipoprotein	2000 ul	X	X	X
Aspartate transaminase, Alanine transaminase	2000 ul	X	X	X
IL-6, IL-15	2000 ul	X	X	X
25-hydroxyvitamin D	1000 ul	X	X	X
Hematocrit	500 ul	X	X	X

Total volume of blood per visit	~ 20 ml	20 ml	20 ml	20 ml
---------------------------------	---------	-------	-------	-------

After taking the blood samples a snack will be provided to the participants in order to complete the following tests.

1. Hand-grip strength: previously described in the screening point
2. Short Physical Performance Battery (SPPB): the SPPB score will be based on three tests, as follows: balance test, gait speed test, and chair stand test (see **Attachment E**). Of note, these tests have been used as a predictive tool for possible disability and can aid in the monitoring of function in older people.

Following, the subjects will randomize into the study supplement: a) Placebo powder (46 g placebo powder in 180 ml of water); or b) freeze-dried table grape powder (46 g grape powder in 180 ml of water). The supplement will be supplied to the participants to complete the following 3 weeks supplementation until the next visit. The investigator or designee will explain the details regarding the preparation and consumption of the supplement [a dosing protocol will be uploaded too (**Attachment F**)].

Also a 24-hs food and physical activity questionnaire will be performed

Briefly, at visit 1:

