- Subjects will arrive fasted for at least 12 h prior to this visit (water ok).
- A finger stick blood sample will be collected (to confirm fasting).
- Concomitant medications and accomplishment of inclusion and exclusion criteria will be reviewed.
- 24-hs food and physical activity questionnaire
- Seated resting blood will be measured.
- Weight will be measured.
- Venous blood samples will be collected for analytical determinations (20 ml).
- A hematocrit will be performed in order to discard anemia.
- Snack ingestion
- Hand grip strength and SPPB test will be completed.

- The supplement will be provided to the subjects for a 3 weeks supplementation period.
- Stool and urine collection kit and a standardized log and instructions (**Attachment G and H**) will be provided to subjects. The kits will be returned at visit 2.

Visit 2 (3-weeks visit):

Subjects will return to the Ragle Facility for the follow-up visit. This visit will take approximately 2 h to complete.

Briefly, at visit 2:

- Subjects will arrive fasted for at least 12 h prior to this visit (water ok).
- Subjects will provide fecal and urine samples collected with the collection kit.
- A finger stick blood sample will be collected (~1 drop).
- Concomitant medications and accomplishing of inclusion and exclusion criteria will be reviewed.
- 24-hs food and physical activity questionnaire
- Seated resting blood pressure will be measured.
- Weight will be measured.
- Subjects will take the assigned supplement.
- Venous blood samples will be collected (20 ml).
- A hematocrit will be performed in order to discard anemia.
- Snack will be provided to the participants.
- Hand grip strength and SPPB test will be completed.
- Enough supplement will be provided to the subjects for a 3 weeks supplementation period.
- Unused and empty packages of the study product will be return.
- Stool and urine collection kit will be provided to subjects. The kits will be returned at visit 3.

Visit 3 (final visit):

Subjects will return to the Ragle Facility for the final visit. This visit will also take approximately 2 h to complete.

Briefly, at visit 3:

- Subjects will arrive fasted for at least 12 h prior to this visit (water ok).
- Subjects will provide fecal and urine samples collected with the collection kit.
- A finger stick blood sample will be collected (~1 drop).
- Concomitant medications and accomplishing of inclusion and exclusion criteria will be reviewed.

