- 24-hs food and physical activity questionnaire
- Seated resting blood pressure will be measured.
- Weight will be measured.
- Subjects will take the assigned supplement.
- Venous blood samples will be collected (20 ml).
- A hematocrit will be performed in order to discard anemia.
- Snack will be provided to the participants.
- Hand grip strength and SPPB test will be completed.
- Unused and empty packages of the study product will be return.

10) Study Timelines

Duration of individual subject's participation will be ~6 weeks. The study will include: 1 visit (visit 0) for the screening process that will last approximately 2 h and 3 more visits (visits 1, 2 and 3) for intervention process that will last approximately 2 h each. Visit 0 will involve an in-person screening to obtain written informed consent and determine if subjects meet the inclusion/exclusion criteria. Visit 1, 2 and 3 (at 0, 3 weeks and at the end of the 6 weeks, respectively) will include blood sample collection and tests performance.

11) Study Endpoints

Primary endpoint:

Hand-grip strength media value of 16 kg or lower

Secondary endpoints:

Levels of Irisin as a marker of sarcopenia

Glucose, Insulin, GLP-1, GLP-2, GIP, Adiponectin, leptin and ghrelin, Blood urea nitrogen, creatinine, Aspartate transaminase, Alanine transaminase, Total cholesterol, triglyceride, high-density lipoprotein (HDL), low-density lipoprotein, IL-6, IL-15, 25-hydroxyvitamin D as markers of general metabolism state.

12) Data and/or Specimen Management and Confidentiality

Data management: The de-identified data will be analyzed for statistical significance with the help of the Biostatistics group at UC Davis, including univariate graphical, analytic summaries and bivariate relationships using box plots, scatter plots, and correlations. To compare participants in the two diet groups (Placebo control and freeze-dried table grape powder) a paired Student's t test (two-tailed) will be used. Data involving more than two repeated measures, such as grip strength tasks, or irisin levels, will be assessed by repeated measures (ANOVA). Differences will be considered significant at $P < 0.05$. Significant results will be also subjected to analysis of covariance (ANCOVA) to account for group differences at baseline and post hoc comparisons using the Bonferroni correction.

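### Two independently randomised arms are sized and compared with a paired t-test, so the stated between-group test has no pairs and the 80% power at 5 per group is unsupported

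*Protocol*

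**What the plan says.** **Design.** In Section 9, at visit 1, "the subjects will randomize into the study supplement: a) Placebo powder" or grape powder. At visits 2 and 3 the instruction is "Subjects will take the assigned supplement". Section 10 describes one period of about 6 weeks. No crossover, second period or matching appears anywhere.

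**Sizing.** Section 4 takes the change in plasma irisin as its outcome and states that "5 individuals per group are required to reach 80% power to detect differences in irisin levels between the groups", at a 0.05 level, "using a two-sided paired T-test". It enrols 7 per group (14 in all) to allow for dropout. The basis is preliminary data in reference 11. No difference, SD or correlation is given. Section 3 describes that work as showing that phenolic compounds in a grape pomace extract "prevent irisin downregulation in rats fed a high-fat diet and in L6 myotube cells".

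**Analysis.** Section 12 says: "To compare participants in the two diet groups (Placebo control and freeze-dried table grape powder) a paired Student's t test (two-tailed) will be used". It then assigns data with more than two repeated measures, with grip strength and irisin as examples, to repeated-measures ANOVA, and adds: "Significant results will be also subjected to analysis of covariance (ANCOVA) to account for group differences at baseline".

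**The concern.** A paired t-test needs a natural link between each observation in one group and one observation in the other. Here the groups are different women allocated at random, so no such link exists. The sentence in Section 12 can be followed in only two ways:

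- **Pair women across arms arbitrarily.** The p-value then depends on who is paired with whom, half the degrees of freedom are lost, and unequal arms after dropout cannot all be used.
- **Pair each woman with her own baseline.** The test then looks within one arm and does not compare the arms. Any change common to both arms (practice on the grip test, season, trial participation) would be credited to the grape powder, and the placebo group would not serve as a control.

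The sizing has the same fault. The stated power belongs to a design this trial does not have, and a reader cannot tell whether the two extra women per arm are a real reserve against dropout or are needed to reach 80% at all.

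**Working it through.** **Inputs.** From Section 4: two-sided level 0.05, power 80%, 5 per group required, 7 enrolled, paired t-test. From Section 9: two arms, each woman in one arm only. The documents give no effect size, SD or correlation, so the figure of 5 cannot be reproduced forwards. I solved backwards with exact noncentral-t power.

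**Formulas.**
- Paired, n pairs: df = n − 1, noncentrality = dz × √n, where dz is the mean difference divided by the SD of the within-pair difference.
- Two-sample, n1 v n2: df = n1 + n2 − 2, noncentrality = d × √(n1·n2/(n1 + n2)), where d is the difference divided by the common SD.
- Power = probability that the noncentral t exceeds the two-sided 5% critical value (the opposite tail is negligible).

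**Step 1: what the stated 5 implies if the test was paired.** With n = 5 (df 4, critical value 2.776), 80% power needs dz = 1.682. With n = 4 (df 3, critical value 3.182), it needs dz = 2.128. So 5 is the required number of pairs for dz from 1.68 to just under 2.13.

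**Step 2: the same standardised effect in two independent arms.** Assumption: d = dz, which corresponds to a correlation of 0.5 behind the paired figure.

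| Completers per arm | Power at 1.682 | Power at 2.128 |
|---|---|---|
| 5 v 5 | 64.6% | 83.7% |
| 7 v 5 | 73.6% | 90.5% |
| 6 v 6 | 74.7% | 91.2% |
| 7 v 7 | 82.3% | 95.4% |

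Example, 5 v 5 at the low end: noncentrality = 1.682 × √(25/10) = 2.66, df 8, critical value 2.306, power 64.6%.

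**Step 3: completers needed.** The two-sample effect detectable with 80% power is 2.38 SD at 4 per arm, 2.02 at 5, 1.80 at 6 and 1.63 at 7. Across the range in Step 1, the number needed is therefore 7 per arm at the low end (about 1.68 to 1.79), 6 in the middle (1.80 to 2.02) and 5 at the top (2.03 to 2.13). At the low end no dropout reserve remains.

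**Step 4: sensitivity to the assumed correlation.** If dz came from pairs with correlation ρ, then d = dz × √(2(1 − ρ)).
- ρ = 0: factor 1.414, d = 2.38 to 3.01; power at 5 per arm 90.7% to 98.5%.
- ρ = 0.8: factor 0.632, d = 1.06 to 1.35; power at 5 per arm 31.7% to 46.5%, and at 7 per arm 44.9% to 63.8%.

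**Step 5: if *paired* is only a slip of wording.** A two-sample calculation gives 5 per arm for an effect from 2.02 to just under 2.38 SD.

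**Step 6: cost of arbitrary pairing at 7 v 7.** The SD of a difference between two unrelated women is √2 times the SD of one. Seven pairs need dz = 1.273, so the detectable effect is √2 × 1.273 = 1.80 SD with 6 df, against 1.63 SD with 12 df unpaired. At 1.63 SD, power is 72% instead of 80%. In a simulation of 7 v 7 independent normal samples with no effect, arbitrary pairing rejected in 5.0% of runs, so type I error is not inflated.

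**The case against.** The strongest reply is that the paired test may hardly be used. Grip strength, SPPB and every plasma marker are measured at visits 1, 2 and 3. All of them have more than two repeated measures and could go to the repeated-measures ANOVA; the mention of baseline group differences suggests that groups would be compared there. This softens the point without removing it. The ANOVA sentence names no group factor or group-by-time term. ANCOVA, the natural between-arm analysis, is run only on results that are already significant. The paired t-test remains the one method the text assigns to the two-group comparison, and none of this touches Section 4.

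Second, the before/after reading fits the text poorly, because both sections speak of a contrast between groups. That is fair. The within-arm harm arises only if someone resolves the contradiction that way.

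Third, the loss from arbitrary pairing is moderate (72% v 80% power) and type I error holds. That stands. The main harm is an undefined test whose p-value depends on an arbitrary choice.

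Fourth, the power could be understated as easily as overstated. With zero correlation, 5 per arm gives over 90%, and nothing in the protocol points to a correlation of 0.8. This also stands, and it is why the conclusion goes no further than unsupported.

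Finally, this is a pilot. That limits what the power statement has to carry, but it does not make a paired comparison of independent arms usable.

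**Conclusion.** The concern holds. The protocol describes independent arms and assigns a paired test to the comparison between them, both in sizing and in analysis. As written, the two-group test cannot be carried out validly, and this must be corrected before analysis.

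The contradiction rests on the text alone. The size of the power problem rests on assumptions: if the 5 came from a paired test and the same standardised effect carries over, power is 65% to 84% at 5 completers per arm and 82% to 95% at 7. Over assumed correlations from 0 to 0.8, power at 5 per arm runs from about 32% to 98.5%. If the calculation was really two-sample, 5 per arm is correct for an effect of at least 2.02 SD. The stated 80% is thus neither confirmed nor refuted.

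**What to change.** **Section 12.** Replace the paired t-test with an independent-groups comparison. The recommended form is ANCOVA of the week-6 value on arm and visit-1 value, run whatever other tests show. A Welch t-test on change from visit 1 is an acceptable minimum. If repeated-measures ANOVA is kept to use the week-3 data, name arm and arm-by-visit as terms and say which term is the between-arm test.

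**Section 4.** State the assumed difference and SD of the irisin change and that they come from reference 11 (rat and cell data). Recalculate for two independent groups, and give the power at 5 and at 7 completers per arm. If the calculation was already two-sample, delete *paired* there and say so. Section 4 calls irisin the primary outcome while Section 11 lists it as secondary to grip strength, so state which endpoint the recalculation serves.

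**Cost.** Wording in two sections and one recalculation, with no new procedures. The stated power may become less favourable. If it falls below 80% with 7 completers per arm, the sponsor would have to accept that openly or enrol more women.

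### Every listed endpoint falls under both the t-test rule and the repeated-measures ANOVA rule at P < 0.05, and the protocol does not say which one decides; if either may, the false-positive rate per endpoint is about 6-15%

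*Protocol*

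**What the plan says.** Section 12 (Data and/or Specimen Management and Confidentiality) gives two analysis rules and one threshold.

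- Rule 1 has no restriction: "To compare participants in the two diet groups", placebo and grape powder, "a paired Student's t test (two-tailed) will be used".
- Rule 2 is: "Data involving more than two repeated measures, such as grip strength tasks, or irisin levels, will be assessed by repeated measures (ANOVA").
- The significance threshold is P < 0.05, with no division between the two rules.
- A follow-up step is added: "Significant results will be also subjected to analysis of covariance (ANCOVA) to account for group differences at baseline and post hoc comparisons using the Bonferroni" adjustment.

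Section 9 (Visit 1) lists the plasma markers and notes that "the same parameters will be measure in the following visits 2 and 3". Section 10 says: "Visit 1, 2 and 3 (at 0, 3 weeks and at the end of the 6 weeks, respectively) will include blood sample collection and tests". Grip strength is also taken at screening.

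Section 4 takes change in plasma irisin as the outcome for the sample size and bases it on 80% power at alpha 0.05, "using a two-sided paired T-test".

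**The concern.** Rule 2 reads as if it separated one class of data from another. For the listed endpoints it does not: each is measured at more than two visits, and each is also compared between the two diet groups. Nothing in the protocol ranks the two tests. It does not say which ANOVA term (group or group-by-time) carries the conclusion, or at which visit the t test is done.

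The same endpoint can therefore be significant by one route and not by the other. With 14 women, that choice, if made after seeing the data, can settle whether irisin or grip is reported as improved. Section 2 intends the results as preliminary evidence for a competitive grant application. At stake is whether the 5% error rate used in Section 4 holds even for a single outcome chosen in advance.

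**Working it through.** **1. Do the two rules overlap?** Section 11 lists grip, irisin and 19 further markers: 1 + 1 + 19 = 21 endpoints. Sections 9 and 10 measure the blood markers at visits 1, 2 and 3 (three values) and grip at visits 0 to 3 (four values). All 21 have more than two repeated measures, and all 21 are two-group comparisons. Irisin is assigned a paired t-test in Section 4 and is named for ANOVA in Section 12.

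**2. The plan's own figure.** Section 4 states 5 per group for 80% power but gives no effect size or SD, so it cannot be reproduced. Solving the noncentral t distribution backwards, n = 5 at 80% power implies a standardised effect of 1.68 (5 pairs) or 2.02 (two independent groups of 5). The stated alpha belongs to a single test.

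**3. Benchmark.** For k independent tests at 0.05 the chance of at least one false positive is 1 - 0.95^k: 1 - 0.95^2 = 9.75% and 1 - 0.95^3 = 14.3%. The tests here are correlated, so simulation is needed.

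**4. Null simulation.** Inputs from the protocol: 7 per arm, visits 1, 2 and 3, two-sided 0.05. Assumed, because the protocol does not give them: normal data and a within-woman correlation of 0.3-0.9 (compound symmetry) or 0.5-0.9 (AR(1)). There were 100,000 trials per setting. The t-test was run both paired as written (arbitrary pairs, 6 df) and as independent groups (12 df). The ANOVA group term has 1 and 12 df, and the group-by-time term 2 and 24 df. A false positive is counted when the smallest P among the listed tests is below 0.05.

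| Tests that may each declare significance | False-positive rate |
|---|---|
| One t-test | 4.9-5.1% |
| ANOVA group-by-time term only | 4.9-5.1% (up to 5.7% under AR(1) with no sphericity correction) |
| Week-6 t-test on level, or group term | 6.2-8.6% |
| Week-6 t-test on change, or group-by-time | 6.5-8.1% |
| Week-6 t-test on level, or group-by-time | 9.0-10.2% |
| Week-6 t-test on change, or group term | about 9.6-9.8% |
| One week-6 t-test, or either ANOVA term | 10.9-12.7% |
| Week-3 and week-6 t-tests on level, or either ANOVA term | 12.0-15.3% |

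**5. Other readings of the same text.**

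- ANOVA alone, with either the group or the group-by-time term counting: about 10%.
- Either test, but ANCOVA must also be significant (60,000 trials per setting, compound symmetry): 2.3-4.0%.
- The t-test and the group-by-time term both required: 0.3-2.4%.

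**6. Does pairing cause the inflation?** No. The paired test on arbitrary pairs holds about 5% under the null. Its cost is power. Assume a correlation of 0.5 and a week-6 effect of 1.2 SD. The change score then has an SD of 1, and a difference between two changes has an SD of √2. The standardised effect is 1.2/√2 = 0.849, the noncentrality is 0.849 × √7 = 2.25, and the power on 6 df is 47%. ANCOVA on the same simulated data gives 62% and holds 5% under the null.

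**The case against.** The strongest objection is that the protocol never says either result suffices, or that both tests are run on each endpoint. Rule 2 can be read as an exception to Rule 1, so that data with more than two measures go to ANOVA alone; the rate is then about 5-6% for one term. This stands as a limit on the size of the problem, but it does not remove the problem. On that reading the t-test applies to no listed endpoint, it still contradicts Section 4 for irisin, and the ANOVA term remains open (about 10% if either counts).

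A second objection is the ANCOVA step. If it must confirm, the rate falls below 5%. The text says only that significant results also go to ANCOVA, not that ANCOVA decides. Bonferroni is attached to the post hoc comparisons, not to the choice between tests.

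Third, the upper end needs a week-3 t-test and two ANOVA terms that Section 12 does not name. That is correct. One t-test with one ANOVA term gives 6.2-10.2%.

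Fourth, Rule 2 might separate something after all: stool and urine are returned only at visits 2 and 3. No stool or urine measure is a listed endpoint. Also, Section 11 words the grip endpoint as a threshold, to which neither test applies as written, so the rates above are for grip analysed in kilograms.

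Fifth, the choice of term and visit may be left to the SAP. An omission of that detail would be no finding. Here the protocol has itself fixed two tests that collide.

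**Conclusion.** The point holds as a defect in the stated rules. All 21 listed endpoints meet both rules at the same threshold with no order between them, and for irisin Sections 4 and 12 name different tests.

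A reader might infer that the false-positive rate per endpoint simply is 7-15%. The documents do not support that, because it presupposes a rule under which either result counts, which the protocol does not state. The supportable statement is conditional: about 6-15% if either test may declare significance, with the top of the range needing two t-tests plus two ANOVA terms; about 5-6% if one ANOVA term is used; below 5% if ANCOVA must confirm. These figures rest on 7 per arm, normal data and an assumed within-woman correlation of 0.3-0.9. That spread of results follows from a choice the protocol leaves open.

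**What to change.** In Section 12, replace the two rules with one. For each endpoint the deciding test is a single comparison between independent groups at week 6, adjusted for the visit 1 value (ANCOVA). It is carried out whether or not another test is significant first. Label the week-3 comparison and the ANOVA terms as supportive, with no significance claim. Change the test named in Section 4 to match.

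The cost is a few sentences and no new data, since the visit 1 and week-6 values are already collected and ANCOVA is already in the plan. The downside is that the sponsor gives up alternative routes to P < 0.05.

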15) Potential Benefits to Subjects

No direct benefits to the individual subjects are anticipated. However, subjects will receive general information regarding their overall health status.

16) Provisions to Protect the Privacy Interests of Subjects

Subjects will be assigned an identification number (ID) and all data and specimens will be collected and stored using this ID number. Personal information (name, phone number and email address) and consent forms will be kept in confidence and will be stored in a locked cabinet in the investigator's office. The key linking the subjects' personal information to their laboratory results will be kept separately in another locked drawer in the investigator's office (See above for more on confidentiality).

At the Ragle Facility, the subjects will interact with the study coordinator and trained research personnel. The data collection (anthropometry, blood pressure and venipuncture) will be performed in individual secluded rooms by trained research personnel. We will ensure that the subjects feel comfortable with all research procedures. Questions and interactions between the subjects and the research team will be kept private.

17) Sharing of Results with Subjects

Subjects will receive the results of their blood screen (once reviewed and approved) at the time of completion of the study (or early withdrawal). The research data will not be shared with the subjects, but a summary of the research can be provided to the subjects who express interest.

18) Data/Specimen Banking

All samples, including those sent out for outside analysis will have only a numerical identifier and date/time. Specimens to be stored on site will be kept frozen at -80°C in secure laboratories. Specimens will be stored as long as they are viable for analyses; records of storage will be kept by the investigator's lab staff; all records will be of the de-identified specimens. During analyses, the de-identified data will be entered in Excel

files and analyzed for statistical significance using SAS in password protected computers.

19) Multi-Site Research

This is a single site study.

20) Community-Based Participatory Research

N/A

21) Review Requirements

Some research projects require specific IRB determinations.

1. Are there any contractual obligations or other considerations that require IRB review of this research, or review at intervals other than those required by the Common Rule or FDA?

Yes

No

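### Grip strength and irisin are assigned to repeated-measures ANOVA, with baseline adjustment only after significance; one pre-specified baseline-adjusted mixed model would use the same data better

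*Protocol*

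**What the plan says.** Section 12 (Data and/or Specimen Management and Confidentiality) names three methods.

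- For the two groups: "a paired Student's t test (two-tailed) will be used". A paired test does not fit two independent groups; that is a separate point.
- For outcomes over several visits: "Data involving more than two repeated measures, such as grip strength tasks, or irisin levels, will be assessed by repeated measures (ANOVA"). Sections 9 and 10 place these visits at weeks 0, 3 and 6.
- For baseline: "Significant results will be also subjected to analysis of covariance (ANCOVA) to account for group differences at baseline". The threshold that opens this step is "Differences will be considered significant at $P < 0.05".

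Section 4 (Enrollment Numbers) states that "5 individuals per group are required to reach 80% power to detect differences in irisin levels between the groups", and then: "We propose to enroll 7 individuals per group, instead of 5, in the event of a patient drop out of the study". Section 13 (Withdrawal of Subjects) allows removal during the study for, among other things, anemia, supplement use, and glucose or cholesterol above the entry limits. Section 18 says only that data are "analyzed for statistical significance using SAS" and names no procedure. The protocol gives no rule for women with an incomplete set of visits.

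**The concern.** Two features of the named method cost information in a 14-woman trial.

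First, the part of a repeated-measures ANOVA that tests treatment is the group-by-time interaction. Over three visits it has two degrees of freedom and treats baseline as one of the outcomes. It asks whether the arms differ in any pattern over time, not whether they differ at the end of treatment. The baseline-adjusted comparison, which answers that question more directly, is run only if something is already significant. It can confirm or weaken a positive result but cannot reveal an effect that the first test missed.

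Second, the classical form of the method needs all three values. A woman seen at weeks 0 and 3 but not at week 6 drops out of the analysis entirely. Inclusion criteria and hematocrit are checked at visit 2, where grip and irisin are also recorded, so a removal under Section 13 can produce exactly this pattern.

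At stake are the power for grip and irisin and, to a lesser degree, the use of values already collected.

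**Working it through.** **The plan's own figure.** The 5 per group in Section 4 cannot be reproduced, because neither the effect nor the SD is given. Solving the noncentral t for 80% power at two-sided 0.05 shows what it implies: a standardised difference of 2.02 for two samples of 5, or 1.68 for 5 pairs. Going from 5 to 7 allows for 2 of 7 losses per arm (2/7 = 28.6%).

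**Assumptions (none is in the protocol).** SD 1 at each visit; equal correlation ρ between visits, 0.5 to 0.9; arm differences of 0, 0.4 and 0.8 SD at weeks 0, 3 and 6; two-sided 0.05; n per arm.

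**Interaction test.** Noncentrality λ = (n/2) × Σ(δⱼ − mean δ)² / (1 − ρ), with 2 and 2(2n − 2) degrees of freedom. The mean difference is 0.4, so the sum is 0.16 + 0 + 0.16 = 0.32. For n = 7: λ = 3.5 × 0.32 / (1 − ρ) = 1.12 / (1 − ρ), on 2 and 24 df.

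**Baseline-adjusted week-6 test.** Noncentrality 0.8 / √[(2/n)(1 − ρ²)], with 2n − 3 df, averaged over chance baseline imbalance. For n = 7 and ρ = 0.8: 0.8 / √(0.2857 × 0.36) = 2.49, on 11 df.

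| n per arm | ρ | λ | Interaction, formula (simulation) | Adjusted week 6, formula (simulation) |
|---|---|---|---|---|
| 7 | 0.5 | 2.24 | 22% (21%) | 33% (34%) |
| 7 | 0.8 | 5.60 | 50% (50%) | 59% (58%) |
| 7 | 0.9 | 11.2 | 81% (82%) | 85% (86%) |
| 5 | 0.8 | 4.00 | 35% (33%) | 40% (39%) |

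**Where the gain comes from.** A plain t test of change to week 6 has noncentrality 0.8 / √[(2/7) × 2(1 − ρ)] on 12 df. Its power is 28%, 58% and 87% at ρ = 0.5, 0.8 and 0.9. At low correlation both the single contrast and the baseline adjustment help. From about 0.8 the single contrast does the work.

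**Retained data, losses after visit 2.** With 2 losses per arm after visit 2, classical ANOVA uses 10 women and 20 post-baseline values; a mixed model uses 24. Under equal correlation, the correlation of weeks 3 and 6 given baseline is r = ρ/(1 + ρ). The week-6 variance relative to completers only is

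[(1 − r²)/5 + r²/7] / (1/5) = 1 − (2/7)r².

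- ρ = 0.6: r = 0.375, ratio 0.960.
- ρ = 0.8: r = 0.444, ratio 0.944.
- ρ = 0.9: r = 0.474, ratio 0.936.

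The saving is about 4-6% (3% at ρ = 0.5). For the average of weeks 3 and 6, the completers-only variance is 1.24 to 1.27 times that of the mixed model.

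**Losses before visit 2.** Both methods use 20 post-baseline values. There is no gain.

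**Sensitivity to the assumed effect.**
- If the 0.8 SD effect is already complete at week 3, Σ = 0.427. Interaction against adjusted week 6 (n = 7) is then 29% against 33% at ρ = 0.5, 45% against 45% at 0.7, 63% against 59% at 0.8, and 91% against 85% at 0.9. The adjusted average of weeks 3 and 6 from the same mixed model has 46%, 59%, 73% and 93%.
- With the 2.02 SD effect implied by Section 4, rising linearly, both tests exceed 99% at ρ = 0.8 with 7 per arm.

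**The case against.** The strongest reply is that this asks for detail that belongs in an analysis plan. Complete-case use is a property of classical repeated-measures ANOVA, not a sentence in the protocol, and SAS can fit repeated measures in more than one way. That stands: a reader might infer that the protocol restricts the analysis to women with all three visits, and it does not say so. It does fix the method by name and makes baseline adjustment conditional on significance, and those choices can be judged as written.

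A reader might also infer that drop-out is expected. Section 4 only makes room for it and gives no rate.

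A reader might compare 36% power (interaction, 5 completers per arm, ρ = 0.8) with 59% (adjusted week 6, 7 per arm) and credit retained data. That comparison changes the test and the sample size together. At 7 per arm the contrast is 50% against 58-59%. The case in which retained data help most, where two women per arm miss only visit 2 and return (variance down 1 − 5/7 = 29%), has little support: Section 4 speaks of drop-out, and visit 2 is where the second three-week supply is dispensed.

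Finally, a reader might infer that a mixed model removes the bias from Section 13 removals. Those depend partly on glucose, cholesterol and hematocrit, which the model would not contain. It may reduce such bias but cannot be relied on to remove it. The group-by-time test is itself valid in a randomised trial; the complaint is about efficiency.

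**Conclusion.** The point holds as one of efficiency and pre-specification. For an effect of 0.8 SD that grows to week 6, the named omnibus test has about 21%, 50% and 82% power at correlations 0.5, 0.8 and 0.9 with 7 per arm, against 34%, 58% and 86% for a baseline-adjusted week-6 comparison. Most of the gain comes from asking one focused question and from adjusting for baseline unconditionally. Keeping week-3 values of women who leave later adds only about 4-6% in week-6 variance.

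The size rests on assumed correlation, effect and shape. If the effect is complete by week 3 and the correlation is 0.8 or more, the week-6 comparison alone no longer has the advantage, though the average of the two visits from the same model does. At an effect near 2 SD and correlation 0.8 the choice hardly matters. The documents do not support a claim that the protocol mandates complete cases, or that the present method produces a demonstrated bias.

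**What to change.** In Section 12, for grip strength and irisin, replace the repeated-measures ANOVA and the significance-dependent ANCOVA with one pre-specified model:

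- a linear mixed model for the visit 2 and visit 3 values, with visit 1 value, arm, visit and arm-by-visit as fixed effects;
- unstructured covariance over the two visits, REML, and Kenward-Roger degrees of freedom, which matter at this sample size;
- every randomised woman with at least one post-baseline value included;
- the arm difference at week 6 reported with its confidence interval, whether or not any other test is significant. If an effect by week 3 is thought likely, name the average of weeks 3 and 6 in advance as well.

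State that the model assumes data missing at random given the modelled values, and list any removals under Section 13 by arm, visit and reason.

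The cost is a change of analysis text. It needs no extra visits, samples or women, and SAS is already planned. The remaining downside is the missing-at-random assumption, which 14 women cannot test.
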